6. STUDY PLAN AND COLLECTION OF STUDY VARIABLES

6.1 Study Plan

Table 2Study Plan Dose Escalation

	screening	Single dose/Cycle 0 (7 day cycle)			Do	Multip ose/Cyc day cy	ele 1	Cycles 2 -6 (21 day cycle)	Cycle 7 and every 6 weeks onwards	Disconti nuation	28-day follow- up	Progres sion	Details in section		
Day	-28 to -1	D1	D2	D3	D4	D6	D1	D8	D15	D1	D1				
Informed consent	Х														4
Demography & baseline characteristics	Х														6.3.1
Medical/surgical history	Х														6.3.1
Inclusion/exclusion criteria	Х														4
Physical examination	Х	X					Х			Х	X	Х			6.3.2
WHO performance status	Х	Х					Х			Х	Х	Х			6.3.2
Pregnancy test (pre- menopausal females only)	Х														6.3.5
Ophthalmologic assessment	Х														6.3.6
EGFR mutation status (archival tumour tissue)	Х														6.8.1.1
Archival tumour tissue	Х														6.8.1.1
Tumour biopsy (optional)	X								Х			Х			6.8.1.1
Vital signs	X	Х	Х				Х	Х	Х	Х	X	Х			6.3.3
Height	Х														6.3.3
Weight	Х	Х					Х			Х	X	х			6.3.3

Table 2Study Plan Dose Escalation

	screening	Single dose/Cycle 0 (7 day cycle)			Multiple Dose/Cycle 1 (21 day cycle)		Cycles 2 -6 (21 day cycle)	Cycle 7 and every 6 weeks onwards	Disconti nuation	28-day follow- up	Progres sion	Details in section			
Day	-28 to -1	D1	D2	D3	D4	D6	D1	D8	D15	D1	D1				
Clinical chemistry/ Haematology/Urinalysis	X	Х					X	Х	X	Х	Х	Х			6.3.5
ECG	Х	Х	Х				Х	Х	Х	Х	Х	Х			6.3.4
PK blood samples (including metabolites)		Х	Х	Х	Х	Х	X	Х	Х	X (cycle 2 only)					6.6.1
Blood sample for cfDNA	Х	Х									6 wkly at RECI	ST visit		Х	6.8.1.2
Genetics consent and blood sample (optional)	Х														6.8.2
CSF (optional)										X (on	ce only)				6.8.3
RECIST assessments	X						•	Every	y 6 week	cs (relative to fir	st dose of multip	le dosing) ur	ntil progress	tion 🕨	6.10.1
Dispense study medication		X					X			X	X				5
Dose with AZD9291		X					-		1	Daily dosing					5
Concomitant medication	•						•								4.3.1
Adverse events	-														6.4

Table 3Study Plan Phase I Expansion and paired Biopsy Cohorts

	Screening	Dos	Multiple e/Cycle lay cycle	1 (21	Cycles 2-6 (21 day cycle)	Cycle 7 and every 6 weeks onwards	Discontinuation	28-day Follow up	Progression	Detail in section
Day	-28 to -1	D1	D8	D15	D1	D1				
Informed consent	Х									4
Demography & baseline characteristics	Х									6.3.1
Medical/surgical history	Х									6.3.1
Inclusion/exclusion criteria	Х									4
Physical examination	Х	Х			Х	Х	Х			6.3.2
WHO performance status	Х	Х			Х	Х	Х			6.3.2
Ophthalmologic assessment	Х									6.3.6
HRQoL form	Х	х			Every 6 weeks (re first dose) until p		Х		Х	6.5
Pregnancy test (pre-menopausal females only)	Х									6.3.5
T790M mutation status tumour sample (mandatory)	Х									6.8.1.1
Archival tumour tissue	Х									6.8.1.1
Tumour biopsy (Paired biopsy cohort - mandatory)	X			Х						6.8.1.1
Tumour biopsy (optional)	Х			Х			Х			6.8.1.1

Table 3Study Plan Phase I Expansion and paired Biopsy Cohorts

	Screening	Dose	Multiple e/Cycle lay cycle	1 (21	Cycles 2-6 (21 day cycle)	Cycle 7 and every 6 weeks onwards	Discontinuation	28-day Follow up	Progression	Detail in section
Day	-28 to -1	D1	D8	D15	D1	D1				
Vital signs	Х	Х	Х	Х	Х	Х	Х			6.3.3
Height	Х									6.3.3
Weight	Х	Х			Х	Х	Х			6.3.3
Clinical chemistry /Haematology/Urinalysis	Х	Х	Х	Х	Х	Х	Х			6.3.5
ECG	Х	Х	Х	Х	Х	Х	Х			6.3.4
PK blood sample (including metabolites)		Х	Х	Х	X (cycle 2 only)					6.6.1
Blood sample for cfDNA	X	Х			•	6 wkly at R	ECIST visit		Х	6.8.1.2
Genetic consent and blood sample (optional)	X									6.8.2
CSF (optional)					X (once or	nly)				6.8.3
RECIST assessments	Х	•	·		Every 6 weeks (re	lative to first	dose) until progress	ion		6.10.1
Cognitive patient interview (optional)					4-6wks+	4-6 months				6.5.3
Dispense study medication		Х			Х	Х				5
Dose with AZD9291		Daily dosing								5
Concomitant medication	-									4.3.1
Adverse events	4									6.4

Table 4Study Plan Phase II Extension Cohort

	Screening	-	ole Dose/O 1 day cyc	-	Cycles 2-6 (21 day cycle)	Cycle 7 and every 6 weeks onwards	Discontin uation	28-day Follow up	Progress ion	Post progression survival F/U	Detail in section
Day	-28 to -1	D1	D8	D15	D1	D1				6 weekly relative to progression	
Informed consent	Х										4
Demography & baseline characteristics	Х										6.3.1
Medical/surgical history	Х										6.3.1
Inclusion/exclusion criteria	Х										4
Physical examination	Х	Х			Х	Х	Х				6.3.2
WHO performance status	Х	Х			Х	Х	Х				6.3.2
Ophthalmologic assessment	Х										6.3.6
HRQoL form	Х	Х			Every 6 week first dose) unt	s (relative to til progression	Х		Х		6.5
Pregnancy test (pre-menopausal females only)	Х										6.3.5
T790M mutation status tumour sample (mandatory)	Х										6.8.1. 1
Archival tumour tissue	Х										6.8.1. 1

Table 4Study Plan Phase II Extension Cohort

	Screening		ole Dose/(21 day cyc	-	Cycles 2-6 (21 day cycle)	Cycle 7 and every 6 weeks onwards	Discontin uation	28-day Follow up	Progress ion	Post progression survival F/U	Detail in section
Day	-28 to -1	D1	D8	D15	D1	D1				6 weekly relative to progression	
Tumour biopsy (optional)	X			Х			Х				6.8.1. 1
Vital signs	Х	X	Х	X	Х	Х	Х				6.3.3
Height	Х										6.3.3
Weight	X	Х			Х	Х	Х				6.3.3
Clinical chemistry /Haematology/Urinalysis	X	Х	X	Х	Х	Х	Х				6.3.5
ECG	Х	Х	Х	Х	Х	Х	Х				6.3.4
Echocadiogram/MUGA	Х	-	12 v	veekly rel	ative to first d	lose					6.3.7
PK blood sample (including metabolites)		Х	Х	Х	X (cycle 2 only)						6.6.1
Blood sample for cfDNA	Х	Х			6 wkly at RECIST visit X						6.8.1. 2
Genetic consent and blood sample (optional)	X										6.8.2
CSF (optional)		X (once only)								6.8.3	
RECIST assessments	Х	Every 6 weeks (relative to first dose) until progression)									6.10.1

Table 4Study Plan Phase II Extension Cohort

	Screening		ple Dose/C 21 day cyc	-	Cycles 2-6 (21 day cycle)	Cycle 7 and every 6 weeks onwards	Discontin uation	28-day Follow up	Progress ion	Post progression survival F/U	Detail in section
Day	-28 to -1	D1	D8	D15	D1	D1				6 weekly relative to progression	
Cognitive patient interview (optional)					4-0	6wks + 4-6 month	15				6.5.3
Dispense study medication		Х			Х	Х					5
Dose with AZD9291		-			Daily	v dosing					5
Concomitant medication	•										4.3.1
Adverse events											6.4
Survival										Х	6.3.8. 3

6.2 Recording of data

Web Based Data Capture (WBDC) will be used for data collection on the observations, tests and assessments specified in the protocol and query handling. The investigator will ensure that data are recorded on the Case Report Forms as specified in the protocol and in accordance with the instructions provided. These instructions provide guidance for the recording of study data in the CRF including how to change data incorrectly recorded.

The investigator ensures the accuracy, completeness, and timeliness of the data recorded and for the provision of answers to data queries according to the Clinical Study Agreement or applicable information.

The investigator will sign the completed Case Report Forms. A copy of the completed Case Report Forms will be archived at the study site.

For details of data and study management see Appendix E of this Clinical Study Protocol.

6.3 Safety procedures

6.3.1 Enrolment and screening

At enrolment, each potential patient will provide informed consent prior to starting any study specific procedures (see Appendix D of this Clinical Study Protocol for Ethics and Regulatory Requirements).

Each potential patient is assigned a unique enrolment number by a nominated person at AstraZeneca. Recruitment into the study will be conducted in a controlled manner. No patient will be enrolled without prior authorisation from AstraZeneca to ensure adherence with the rolling 6 recruitment design and subsequent allocation to expansion cohorts. If a patient withdraws from the study, then the enrolment code cannot be reused.

Demographic data and other characteristics will be recorded and will include date of birth or age, gender, race and/or ethnicity according to local regulations, smoking history.

A standard medical, medication and surgical history will be obtained with review of the selection criteria with the patient.

Each patient will undergo screening (see Study Plan Table 2, Table 3 and Table 4) during the 28 days prior to admission to confirm eligibility (see Sections 4.1. and 4.2). Tumour assessments and other clinical data obtained as standard of care prior to consent may be used for the study provided the assessments fall within the protocol specified period prior to the first dose of study treatment. Tumour receptor/mutation status will be recorded including EGFRm, T790M and cMET etc.

Prior to discharge from each in-patient and clinic visit, the Investigator or their deputy will be responsible for reviewing all available data including vital signs and ECG tracings.

6.3.2 Physical examination

A complete physical examination will be performed at the visits as indicated in the Study Plan (see Study Plan Table 2, Table 3 and Table 4)

Performance status will be assessed at screening, prior to the first dose of study treatment, at the beginning of each Cycle, and at discontinuation according to WHO criteria as follows:

- 0 = Fully active, able to carry out all pre-disease activities without restrictions
- 1 = Restricted in physically strenuous activity but ambulatory and able to carry out work of a light or sedentary nature eg, light housework, office work
- 2 = Ambulatory and capable of self-care, but unable to carry out any work activities. Up and about more than 50% of waking hours
- 3 = Capable of only limited self-care, confined to bed or chair more than 50% of waking hours
- 4 = Completely disabled, cannot carry on self-care, totally confined to bed or chair

6.3.3 Vital signs

Pulse rate and blood pressure

Supine blood pressure and pulse rate will be measured after 10 minutes rest. Assessments will be performed at the visits as shown in the Study Plan (See Table 2, Table 3 and Table 4). Pulse rate and blood pressure will be recorded at the following times:

- Screening
- First dosing day (Day 1 Cycle 0) for dose escalation cohorts
 - pre-dose, 1, 2, 4, 6, 10 and 24 hours (Day 2) post-dose
- First dosing day (Day 1 Cycle 1) for expansion, extension and paired biopsy cohorts
 - pre-dose, 1, 2, 4, 6 and 10 hours post-dose
- Day 1 Cycle 1 for dose escalation cohorts
 - Pre-dose only
- Day 8 and Day 15, Cycle 1 (Multiple Dosing for all cohorts)
 - Pre-dose only
- Day 1, Cycle 2 (Multiple dosing all cohorts)

- pre-dose, 1, 2, 4, 6, 10 and 24 hours (Day 2) post-dose
- On Day 1 of each subsequent Cycle; one assessment at any time during day
- On occurrence of any cardiac AE
- Discontinuation visit

Weight will be performed at screening and then Day 1 of each cycle and at the discontinuation visit.

Height will be assessed at screening only.

Any changes in vitial signs should be recorded as an AE if applicable.

6.3.4 ECG

Resting 12-lead ECG

Twelve-lead ECG will be performed at the visit indicated in the Study Plan (see Table 2, Table 3 and Table 4).

Twelve-lead ECGs will be recorded at the following times:

- Screening
- First dosing day (Day 1 Cycle 0) for dose escalation cohorts

- pre-dose, 1, 2, 4, 6, 10 and 24 hours (Day 2) post-dose

- First dosing day (Day 1 Cycle 1) for expansion, extension and paired biopsy cohorts
 - pre-dose, 1, 2, 4, 6 and 10 hours post-dose
- Day 1 Cycle 1 for dose escalation cohorts
 - Pre-dose only
- Day 8 and Day 15, Cycle 1 (Multiple Dosing for all cohorts)
 - Pre-dose only
- Day 1, Cycle 2 (Multiple dosing all cohorts)
 - pre-dose, 1, 2, 4, 6, 10 and 24 hours (Day 2) post-dose
- On Day 1 of each subsequent Cycle; one assessment at any time during day

- On occurrence of any cardiac AE
- Discontinuation visit

The timing and number of ECGs may be altered depending on the emerging PK and safety profile.

Twelve-lead ECGs will be obtained after the patient has been resting semi-supine for at least 10 minutes prior to times indicated. All ECGs should be recorded with the patient in the same physical position. For each time point three ECG recordings should be taken at about 5 minute intervals. A standardised ECG machine should be used and the patient should be examined using the same machine throughout the study if possible.

After paper ECGs have been recorded, the investigator or designated physician will review each of the ECGs and may refer to a local cardiologist if appropriate. A paper copy should be filed in the patient's medical records. If an abnormal ECG finding at screening or baseline is considered to be clinically significant by the investigator, it should be reported as a concurrent condition. For all ECGs details of rhythm, ECG intervals and an overall evaluation will be recorded.

All ECG data (with the exception of the screening ECGs) will also be collected digitally and will be transferred electronically for central analysis as described in the study specific ECG manual. Heart rate, PR, R-R, QRS and QT intervals will be determined and reviewed by an external cardiologist.

6.3.5 Laboratory safety assessment

Blood and urine samples for determination of clinical chemistry, haematology and urinalysis will be taken at the visits as indicated in the Study Plan (see Table 2, Table 3 and Table 4). Laboratory tests do not need to be repeated at baseline if the baseline visit is within 7 days of the screening sample.

Blood and urine samples for safety assessment will be collected at the following times:

- Screening
- First dosing day (Day 1 Cycle 0 for dose escalation, Day 1 Cycle 1 for expansions and extension); pre-dose (baseline)
- First day of multiple dosing, Day 1 Cycle 1 dose escalation only; pre-dose
- Multiple dosing, Days 8 and 15 of Cycle 1; pre-dose
- On Day 1 of each subsequent Cycle; pre-dose
- Discontinuation visit

The date of each collection will be recorded in the appropriate CRF.

Following review of data from a group of patients the timing of blood samples may be adjusted for subsequent groups of patient. Additional sampling times may be added if indicated by the emerging data.

Laboratory values that meet the criteria for CTCAEv4 grade 3 or have changed significantly from baseline and are considered to be of clinical concern will be repeated/confirmed within 7 days and followed up as appropriate.

The following laboratory variables will be measured:

Clinical chemistry	Haematology
Serum (S)/Plasma (P)-Albumin	Blood (B)-Haemoglobin
S/P-ALT	B-Leukocyte
S/P-AST	B-Haematocrit
S/P-Alkaline phosphatase	B-Red blood cell (RBC) count
S/P-Bilirubin, total	B-Absolute leukocyte differential count:
S/P-Calcium, total	Neutrophils
S/P-Creatinine	Lymphocytes
S/P-Glucose (fasting on PK days only)	Monocytes
S/P-HbA1C	Basophils
S/P-Magnesium	Eosinophils
S/P-Potassium	B-Platelet count
S/P-Sodium	B-Reticulocytes
S/P-Urea nitrogen	Urinalysis
	U-Glucose
	U-Protein
	U-Blood

Additionally a urine/serum sample will be collected from all females of child bearing potential at screening, before first dose for a pregnancy test.

NB. In case a subject shows an AST or $ALT \ge 3xULN$ or total bilirubin $\ge 2xULN$ please refer to Appendix G 'Actions required in cases of combined increase of aminotransferase and total bilirubin – Hy's Law' for further instructions.

For blood volume see Section 6.9.1

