5. STUDY TREATMENT AND CONDUCT

5.1 Treatment

AZD9291 is planned to be administered orally as a single daily dose (although alternative frequencies or intermittent schedules may be instigated in response to emerging safety, tolerability or PK data).

AstraZeneca will supply AZD9291 as capsules or tablets for oral dosing. Additional information about the investigational product may be found in the Investigators' Brochure.

Investigational product	Dosage form and strength	Manufacturer
AZD9291	20 mg and 40 mg Capsule	AstraZeneca
AZD9291	40mg and 80mg Tablet	AstraZeneca

Capsules and tablets will be packed in high-density polyethylene (HDPE) bottles with childresistant closures. One or more bottles of AZD9291 will be dispensed at each dispensing visit depending on the dose. Bottles will be dispensed to subjects in the AstraZeneca packing provided. The packaging includes bottles, caps and a label. Bottle tampers should not be broken prior to dispensing study drug to a patient. For the Ph II extension cohort an IVRS/IWRS system will be deployed to manage the supply of AZD9291 tablets to sites and to manage the dispensing of AZD9291 to patients. All patients entering the extension cohort will be dispensed the tablet formulation. All other cohorts of patients will continue to be dispensed the capsule formulation.

Labels will be prepared in accordance with Good Manufacturing Practice and local regulatory guidelines. The labels will fulfil Good Manufacturing Practice Annex 13 requirements for labelling. Label text will be translated into local language.

The label will include the Name of the Sponsor, Study Code, For Clinical trial use only and /or any other market specific requirements

All study drugs should be kept in a secure place under appropriate storage conditions. The investigational product label on the pack specifies the appropriate storage.

Patients (with the exception of patients with insulin dependent diabetes) must fast for ≥ 1 hours prior to taking a dose to ≥ 2 hour post dose. Water is permitted during this fasting period.

Patients will be required to fast (water only) for at least 8 hours prior to the collection of a fasting glucose sample as per the study plan, (see Table 2, Table 3 and Table 4).

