Data from all cycles of initial treatment will be combined in the presentation of safety data. AEs will be listed individually by patient and dose group. For patients who have a dose modification, all AEs (due to drug or otherwise) will be assigned to the initial dose group. The number of patients experiencing each AE will be summarised by the Medical Dictionary for Regulatory Activities (MedDRA) system organ class, MedDRA preferred term and CTCAE grade. The number and percentage of patients with adverse events in different categories (eg, causally related, CTCAE grade \geq 3 etc) will be summarised by dose group, and events in each category will be further summarised by MedDRA system organ class and preferred term, by dose group. SAEs will be summarised separately if a sufficient number occur.

Any AE occurring before the first dose of investigational product (ie, before study Day 1) will be included in the data listings but will not be included in the summary tables of adverse events.

Any AE occurring within the defined 28 day follow-up period after discontinuation of investigational product will be included in the AE summaries. Any adverse events in this period that occur after a patient has received further therapy for cancer (following discontinuation of investigational product) will be flagged in the data listings. AEs occurring after the 28 day follow-up period after discontinuation of investigational product will be listed separately, but not included in the summaries.

Haematology, clinical chemistry, vital signs, ECG data, ophthalmic examination data, demographic data and concomitant medications will be listed individually by patient and suitably summarised. For all laboratory variables, which are included in the current version of CTCAE, the CTCAE grade will be calculated. Summary statistics of mean, median, standard deviation, minimum, maximum and number of observations will be used.

Details of any deaths will be listed for all patients.

Any qualitative assessments will be summarised for all patients using the number of patients with results of negative, trace or positive.

Graphical presentations of safety data will be presented as is deemed appropriate. This may include, but is not restricted to, presentation of parameters against time, concentration or shift plots. Appropriate scatter plots will also be considered to investigate trends in parameters compared to baseline.

Pharmacokinetics

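### Glucose must be fasting only on PK days, and the last PK day with chemistry is Cycle 2 Day 1, so glucose grades and trends can confound sampling condition with time on drug

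*Protocol*

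**What the plan says.** Protocol Section 6.3.5 lists glucose in the chemistry panel as "S/P-Glucose (fasting on PK days only". It schedules chemistry at screening, on the first dosing day, on Cycle 1 Day 1 (escalation) and Days 8 and 15, at discontinuation, and "On Day 1 of each subsequent Cycle; pre-dose". It also allows a screening result to serve as baseline: "Laboratory tests do not need to be repeated at baseline if the baseline visit is within 7 days of the screening sample".

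Section 5.1 sets two different fasts. Around dosing, patients other than insulin-dependent diabetics "must fast for ≥ 1 hours prior to taking a dose". For glucose, they must "fast (water only) for at least 8 hours prior to the collection of a fasting glucose sample as per the study plan", with a reference to Tables 2, 3 and 4. Those tables have no entry that marks a fasting glucose sample.

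For analysis, Section 7.9 says: "For all laboratory variables, which are included in the current version of CTCAE, the CTCAE grade will be calculated". It combines safety data from all cycles of initial treatment, names time and shift plots among the possible displays, and adds: "Appropriate scatter plots will also be considered to investigate trends in parameters compared to baseline". It does not mention the fasting state of glucose. Section 6.3.5 asks for the collection date in the CRF but not for fasting status.

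**The concern.** Glucose depends on recent food intake. Here the required sampling condition changes at one fixed point in treatment, the same for every patient, and no comparator arm shares the change. If glucose rises or moves to a higher grade after Cycle 2, the glucose data alone may not show whether the drug or the sampling condition is responsible. The baseline has the same weakness, because some patients will have a Day 1 sample with a required fast and others a screening sample without one.

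Safety and tolerability are the primary endpoint for escalation and expansion, and the sample-size section gives safety as a further purpose of the extension. This is also a data-collection rule. If fasting state is not captured when the sample is drawn, no later analysis plan can separate the values.

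**Working it through.** The protocol gives no figure on this point, so there is none to reproduce. The check sets the chemistry visits (Section 6.3.5, Tables 2 to 4) against the PK days (Tables 2 to 5).

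**Step 1: where a fast is required**

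| Chemistry visit | PK day? | 8-hour fast required? |
|---|---|---|
| Screening | No | No |
| Cycle 0 Day 1 (escalation only) | Yes | Yes |
| Cycle 1 Days 1, 8, 15 | Yes | Yes |
| Cycle 2 Day 1 | Yes | Yes |
| Cycles 3 to 6, Day 1 | No | No |
| Cycle 7 Day 1 and 6-weekly after | No | No |
| Discontinuation | No | No |

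The final PK blood sample in Table 5 is the 24-hour sample on Cycle 2 Day 2, which is not a scheduled chemistry visit. From Cycle 3 onward only the routine fast of at least 1 hour before dosing applies.

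**Step 2: count for an expansion or extension patient treated for 52 weeks**

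- Post-baseline samples with a required fast: weeks 1, 2 and 3, which is 3.
- Post-baseline samples without one: weeks 6, 9, 12, 15, 18, 24, 30, 36, 42 and 48, which is 10.
- Total 3 + 10 = 13. The last sample with a required fast is at week 3.

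**Step 3: change from baseline when the drug has no effect**

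Let d be the mean excess of a non-fasting over a fasting value. Let qB and qV be the shares of baseline and visit samples that are in fact non-fasting. Then the expected change from baseline is d × (qV − qB).

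- Fasting Day 1 baseline (qB = 0): zero at the early PK-day visits, and d × qV later.
- Screening sample as baseline: −d × qB at the early visits, and d × (qV − qB) later. The later term is zero if the two shares are equal and negative if baseline was more often non-fasting.

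The protocol gives none of d, qB and qV. The mix of baselines across patients is also unknown. The change from baseline therefore has no fixed direction or size.

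**Step 4: illustration of the possible range, on assumed inputs**

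Take fasting glucose as normal and a limit k standard deviations above its mean, with d now in standard deviations. With no drug effect, the share of later samples above the limit is (1 − q) × P(Z > k) + q × P(Z > k − d), where q is the share of later samples that are non-fasting.

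| Assumed q and d | k = 1 | k = 2 |
|---|---|---|
| Early visits, or q = 0 | 15.9% | 2.3% |
| q = 0.5, d = 0.5 | 23.4% | 4.5% |
| q = 0.5, d = 1 | 32.9% | 9.1% |
| q = 1, d = 1 | 50.0% | 15.9% |

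For example, q = 0.5, d = 1, k = 2 gives 0.5 × 2.3% + 0.5 × 15.9% = 9.1%. All three inputs are assumptions, and k is not a CTCAE limit because the protocol does not reproduce the CTCAE glucose criteria. The table shows only that the artefact could be nil or material.

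**The case against.** A reader might infer that every glucose value after Cycle 2 is non-fasting, so that hyperglycaemia grades must rise with time on drug. The protocol does not support that. It stops requiring the 8-hour fast but does not call for a fed sample. Later Day 1 samples are taken before the dose, and some patients will be fasting anyway. A patient whose baseline was a screening sample also has the same lack of requirement at baseline and at late visits.

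The wider case against the point has several parts:

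- **HbA1c.** It is in the same panel and does not depend on a fast that morning, and urine glucose is also measured. A sustained glycaemic effect could be cross-checked. This stands, and it rules out saying that a drug effect could never be recognised. It does not correct the glucose grades or shifts themselves.
- **Dose-limiting toxicity.** The scheduled on-treatment chemistry in that window falls on PK days, so fasting is required there. Isolated laboratory changes without clinical significance are not dose-limiting, and most mandated laboratory deteriorations are not reported as adverse events. This stands, and it largely confines the problem to descriptive glucose summaries.
- **Analysis plan and CRF.** Section 7.9 leaves much of the display open, and a split by fasting status could be added in the SAP. The CRF, which is not shown, may already hold a fasting field. This is partly right. The protocol still fixes a collection rule that changes with time on treatment, and an SAP can repair that only if fasting status was captured.

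**Conclusion.** The point holds as a risk of confounding. Fasting is required at 4 chemistry visits in expansion and extension (Cycle 1 Days 1, 8 and 15, and Cycle 2 Day 1) and at 5 in escalation, where Cycle 0 Day 1 is added. It is required at no other scheduled visit, and the protocol states no record of fasting status. Over 52 weeks, 10 of 13 post-baseline samples in an expansion or extension patient are uncontrolled in this respect.

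Neither the direction nor the size of any bias in change from baseline can be derived from the protocol, and the bias may be zero. The conclusion assumes that fasting status is not already collected under CRF instructions that are not shown. The matter concerns glucose only. It leaves the dose-limiting toxicity assessment largely untouched and is partly offset by HbA1c. It is still worth correcting, because the missing information cannot be recovered afterwards and costs little to collect.

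**What to change.** - **Section 6.3.5:** record fasting status (at least 8 hours, yes or no) for every glucose sample, including the one used as baseline. Alternatively, apply the same fast at every scheduled pre-dose chemistry visit and to any screening sample that may serve as baseline.
- **Tables 2 to 4:** mark the samples that are to be fasting, since Section 5.1 already refers to these tables for that purpose.
- **Section 7.9:** present glucose change from baseline, shifts and CTCAE grades by fasting status, and compare fasting values with a fasting baseline. Continue to report and grade non-fasting values separately. Restricting grades to fasting samples could remove up to 10 of the 13 post-baseline values in the 52-week patient and hide late hyperglycaemia.

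The cost is one extra CRF field, or a fast before later Day 1 visits, together with smaller numbers in each glucose summary.
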